Our two proof-of-concept studies and the well-established safety profile of permanent splanchnic nerve blockade in patients with intractable abdominal pain (e.g., due to pancreatitis or cancer) provide the foundation for our study. A body of literature (>3,000 published cases) on non-HF patients suggests that the side effects of permanent splanchnic nerve blockade (surgical or interventional via alcohol injection) are restricted to 48-h post procedure. Most common side effects include orthostatic hypotension (80%) followed by gastrointestinal symptoms (60%). Interestingly, transient orthostatic hypotension due an increase in splanchnic vascular storage capacity, is clinically prevented by aggressive pre-procedural hydration. Historically (1930-1950's) surgical denervation of splanchnic nerves has also been applied in form of the so-called splanchnicectomy for treatment of uncontrolled hypertension. While it was shown to be effective to reduce sympathetic tone and reduce blood pressure, the discovery of antihypertensive medications made this surgical procedure obsolete. Long-term pharmacological blockade of the celiac plexus/splanchnic nerves with Botulinum toxin (BTX) has been previously reported to be safe and effective in a case of refractory hypertension. Finally, our group has extensive experience with neuromodulation which includes the application of BTX to epicardial fat pads for prevention of post-operative atrial fibrillation and stellate ganglion blockade for ventricular arrhythmias. **Together, published evidence and our data indicates the potential importance of splanchnic nerve modulation as a treatment for HF, providing a strong scientific premise for further investigation in this field.**

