## Design & Procedures

- Describe the study, providing detail regarding the study intervention (drug, device, physical procedures, manipulation of the subject or the subject's environment, etc.). Discuss justifications for placebo control, discontinuation or delay of standard therapies, and washout periods if applicable. Identify procedures, tests and interventions performed exclusively for research purposes or more frequently than standard of care. Include alternative therapies, concurrent therapies discontinued per protocol, risk benefit ratio, and use of tissue/specimens. Discuss monitoring during washout periods if applicable. Include brief description of follow-up, if any.

**Study design.** The present study will be a prospective open-label pilot study to help establish feasibility, safety and enable dose finding for BTX. The schedule of events is presented in **Figure 3**. Following a baseline invasive (right heart catheterization) cardiopulmonary exercise testing (CPX) patients will undergo unilateral celiac plexus block (**Figures 2 and 4**), followed by repeat hemodynamic testing in the following 90 minutes. Repeat CPX (with and without hemodynamic testing) will occur at 2, 4, 8 weeks. A 12 month phone call to investigate vital status, HF hospitalizations will conclude the study. Functional testing at baseline and follow up will be supplemented by a series of minimally invasive and non-invasive measures of static and dynamic blood volume distribution (radionuclear plethysmography, bioelectrance, hepatic vein ultrasound), congestion parameters (biomarkers, BVA), autonomic nervous tone (catecholamines,

baroreflex, and heart rate variability) and symptom questionnaires (Likert and Visual Analog scale). Given high volume of patients and right heart catheterizations (>1,000 per year) and our experience with enrolling patients in the preliminary studies, we anticipate to complete recruitment within 2 years.

Figure 2. Splanchnic Nerve Block Procedure (A) and Prior Data of Nerve Blockade in Acute (B) and Chronic Heart Failure (C). \* indicates p<0.05

[figure not shown]

Figure 3. Study Flow

[figure not shown]

Figure 4. Study set-up: Invasive hemodynamic testing

[figure not shown]

Table 1: Schedule of events (CS, clinical study; SOC, standard of care/clinical)

Required Assessment	Pre-Procedure (Day 1)	Baseline (Intra-Procedure)	Block	Post-Block Procedure	48 Hour	Week 1	Week 2	Week 4	Week 8	Month 6	Month 12

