Dose down titration scheme is as following: If BP is too low (newly <90mmHg, independent of heart failure medication changes done clinically) or patient report orthostatic symptoms we will return for the next patient to the preceding lower Botox dose. If symptoms of orthostasis or hypotension are experienced already at the lowest dose we will drop the injection dose to 50 Units (not more than 1.5U/kg) . The effects of ropivacaine are expected to occur as early as 15 minutes and last for 24h. The acute effects will serve as confirmation of procedural success and provide reassurance that BTX was injected in the right location. BTX is a neurotoxin that blocks cholinergic neurotransmission and offers temporary autonomic modulation via ganglionic block. The peak pharmacological properties of BTX are expected at 2 weeks post injection. The estimated duration of BTX effect is up to 4-6 months.

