## Study Interventions

- If not already presented in #4 above, describe study-related treatment or use of an investigational drug or biologic (with dosages), or device, or use of another form of intervention (i.e., either physical procedures or manipulation of the subject or the subject's environment) for research purposes.

The study subjects will participate in the following study tests and procedures:

Invasive Test:

1. Regional nerve block under fluoroscopic guidance: A solution of ropivacaine 12 cc (approximately 2.5 teaspoons) and Botox 75-125 units (approximately 0.25 teaspoons), into the space around a nerve, called the splanchnic nerve, which controls the blood vessels in your intestines. These drugs will be delivered using a long needle placed between the patient's ribs in the mid-region of the back. The placement of the needle will be performed by an anesthesiologist experienced with the needle placement, with the assistance of x-ray guidance. The subject's measurement will be monitored for 60 minutes post-block.
2. Cardiopulmonary exercise: The subject will exercise by pedaling on a bike in a supine position for about 2-5 minutes, before stopping to rest. The catheter will remain in the subject's heart to measure pressures while exercising to provide information about the subject's exercise ability.

Non-Invasive Tests:

1. Vital Signs (Orthostatic vital signs)
2. Imaging with ultrasound, impedance, radiofrequency
  1. Fluid content in the body and lungs: The subject will wear a vest that emits radiofrequency waves to measure fluid content (ReDs Vest). The InBody uses Bioelectrical Impedance Spectroscopy to determine fluid content in the subject's body.
  2. Lung impedance: electrodes will be attached to the subject's upper back and chest to determine the intra-thoracic blood volume (CardioSet)
  3. Arterial stiffness using a brachial cuff. A cuff will be applied to your arm, similar to a blood pressure cuff, and a hand held probe will be placed on your groin and arm. The cuff will inflate and will measure pulse wave changes in your blood vessels (Sphygmocor)
  4. Cardiac Hemodynamics: the PhysioFlow device measures the subject's cardiac output, stroke volume, systemic vascular resistance and left cardiac work index.
  5. Oxygen Utilization: VO2 Master Pro (Oxygen consumption) will be used to measure oxygen consumption during rest and exercise. PortaLite and MOXY will measure oxygen concentration during exercise.

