### Risk/Benefit Assessment

- Include a thorough description of how risks and discomforts will be minimized (per 45 CFR 46.111(a) (1 and 2)). Consider physical, psychological, legal, economic and social risks as applicable. If vulnerable populations are to be included (such as children, pregnant women, prisoners or cognitively impaired adults), what special precautions will be used to minimize risks to these subjects? Also identify what available alternatives the person has if he/she chooses not to participate in the study. Describe the possible benefits to the subject. What is the importance of the knowledge expected to result from the research?

Procedural risks of splanchnic nerve blocks have been extensively studied. Risks associated with this anesthetic nerve block are uncommon. Patients undergoing this procedure have a small risk (<1%) risk of developing local anesthetic systemic toxicity as a complication of regional anesthesia. Symptoms include non-specific central nervous system effects (altered mental status, agitation, seizures) and cardiac arrest. We have now completed 28 cases in the first pilot trial using lidocaine/ropivacaine and found no acute or chronic complications.

Mild complications like local pain at injection site, orthostatic hypotension and gastrointestinal dysmotility are time limited and improve with resolution of the anesthetic block. Severe complications like pneumothorax possibly requiring a chest tube, aortic vessel puncture with retroperitoneal bleed or hematothorax and spinal cord injury with possible paralysis. These are very rare since placement of the needle occurs under fluoroscopic guidance.

Other minor risks can include (in order of report in literature and experience at Duke):

1. Pain at puncture site and intercostal neuralgia
2. Gastrointestinal dysmotility including diarrhea, constipation and abdominal cramping as well as nausea
3. Bleeding at puncture site

We will perform the splanchnic block for chronic heart failure, which is a new indication. The splanchnic nerve block has now been studied by us for acute /chronic heart failure but not been studied in the setting of chronic disease. We do not expect unexpected side effects other than stated above but unexpected side effects cannot be excluded. For safety purposes subjects enrolled in this study will remain monitored for several hours after the SNB and re-examined at 2 weeks.

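### The blood-pressure limb of the dose trigger has no scheduled reading between post-block testing and the first follow-up visit; the 48-hour contact is a phone call of unstated content

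*Combined protocol and SAP*

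**What the plan says.** **The trigger.** In Testing procedures, under the nerve block procedure, the down-titration scheme opens: "If BP is too low (newly <90mmHg, independent of heart failure medication changes done clinically) or patient report orthostatic symptoms". Either limb returns the next subject to a lower BTX dose. No time window is attached. The up-titration scheme in the same section rests dose changes on a 4-week assessment.

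**The drugs.** On the anesthetic: "The effects of ropivacaine are expected to occur as early as 15 minutes and last for 24h". BTX is expected to peak at 2 weeks.

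**Observation after the block.** Three places give three periods:
- Study Interventions: "The subject's measurement will be monitored for 60 minutes post-block".
- Design & Procedures: "followed by repeat hemodynamic testing in the following 90 minutes".
- Risk/Benefit Assessment: "For safety purposes subjects enrolled in this study will remain monitored for several hours after the SNB and re-examined at 2 weeks".

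**Schedule of events (Table 1).** Vitals and orthostatic vitals are marked before the procedure, after the block and at three later visits. The 48-hour cell in those rows is empty. The phone-call row appears to start at 48 hours. The protocol describes only what the 12-month call covers.

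**Expected harm.** Risk/Benefit Assessment lists orthostatic hypotension among mild complications that improve as the anesthetic block resolves. Background & Significance reports that "side effects of permanent splanchnic nerve blockade (surgical or interventional via alcohol injection) are restricted to 48-h post procedure", with orthostatic hypotension at 80%. Its source is "A body of literature (>3,000 published cases) on non-HF patients".

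**The concern.** A rule that turns on a pressure below 90 mmHg needs pressures to act on. The protocol links orthostatic hypotension to an anesthetic that it expects to act for 24 h, yet planned measurement appears to stop within hours and resume at a visit one or two weeks later. In between, the plan can learn of hypotension only through symptoms or an unplanned clinical contact.

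Safety is a stated purpose of this pilot, and Data & Safety Monitoring names hypotension as a signal without saying when it is measured. Subjects may enter with a systolic pressure just above 100 mmHg, including subjects on inotropes, so some start about 10 mmHg from the trigger. At stake are the completeness of the early safety record and a clear basis for calling a dose tolerated.

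**Working it through.** The plan gives no sample size, power or error rate for this rule, so there is no figure to reproduce. The check covers the schedule, the length of the gap, and what the two limbs can see.

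**1. Reading the schedule.** By literal column count the three later vitals visits are weeks 1, 2 and 4. If the columns slipped by one they are weeks 2, 4 and 8. The second reading is likelier: the nerve block section places the follow-up tests at weeks 2, 4 and 8, Risk/Benefit Assessment puts re-examination at 2 weeks, and the paid visits are the procedure, 2 weeks and 2 months. Two things hold on both readings: the vitals rows have no mark at 48 hours, and weeks 2 and 4 are covered. One row has lost its label and appears to carry a mark at 48 hours. It may be a phone call or another assessment, so the reading stays provisional.

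**2. Time without a planned reading.** For h hours of monitoring, the unmeasured share is (24 - h)/24 of the anesthetic effect and (48 - h)/48 of the first 48 h. The protocol does not define several hours; 3 and 8 h are assumptions.

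| h | Source | Share of 24 h | Share of 48 h |
|---|---|---|---|
| 1 | Study Interventions | 23/24 = 96% | 47/48 = 98% |
| 1.5 | Design & Procedures | 22.5/24 = 94% | 46.5/48 = 97% |
| 3 | assumed | 21/24 = 88% | 45/48 = 94% |
| 8 | assumed | 16/24 = 67% | 40/48 = 83% |

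**3. What the symptom limb can catch.** Let p be the chance of early hypotension in a subject and s the share of events that cause symptoms and are reported at the call. Subjects are dosed in pairs. The chance that at least one of two is caught is 1 - (1 - ps)^2.

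| s | p = 30% (assumed) | p = 80% (literature figure) |
|---|---|---|
| 0.25 | 0.14 | 0.36 |
| 0.50 | 0.28 | 0.64 |
| 0.75 | 0.40 | 0.84 |
| 1.00 | 0.51 | 0.96 |

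The call is therefore not worthless, but how much it catches depends on s, and the plan does not say what is asked.

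**4. Why the window matters.** If every early event counted, the chance that at least one of two subjects sets off the trigger is 1 - (1 - p)^2: 0.19 at p = 10%, 0.51 at 30%, 0.75 at 50% and 0.96 at 80%. This holds whatever the BTX dose, because the anesthetic alone could produce the events. The rule therefore behaves very differently according to whether anesthetic-period events count, and the plan does not say.

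**5. The rate p is unknown for this block in heart failure.** The 80% comes from permanent surgical or alcohol blockade in patients without heart failure. Risk/Benefit Assessment reports no complications in 28 lidocaine/ropivacaine cases. If orthostatic hypotension was counted there (not stated), the one-sided 95% upper bound is 1 - 0.05^(1/28) = 10.1%.

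**The case against.** The strongest reply is that the rule titrates BTX, not the anesthetic. BTX peaks at 2 weeks, dose changes rest on the 4-week assessment, and vitals and orthostatic vitals fall at weeks 2 and 4 on either reading of Table 1. Orthostatic vitals are also marked after the block, when ropivacaine may already be acting, and Data & Safety Monitoring has data recorded after each subject for signs that include hypotension. The 48-hour call serves the symptom limb. Background & Significance adds that hydration before the procedure is used clinically to prevent the orthostatic effect. How long to observe a patient after a block is a clinical judgement, and observing for less time than a drug acts is not in itself a contradiction.

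Most of this stands. A reader might infer that the trigger is blind when most needed, that early hypotension cannot be counted at all, or that 80% of these subjects should be expected to have it. The documents support none of these: pressure is measured under the block and again around the BTX peak, symptoms have a route in, and the 80% belongs to another procedure in another population.

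What remains is narrower. Hypotension without symptoms after discharge has no planned route into the record, and the trigger does not say whether such an event would count. The 60-minute, 90-minute and several-hours periods may describe different activities, but the protocol does not say so.

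**Conclusion.** The point holds in a limited form. As far as Table 1 can be read, the pressure limb has no scheduled data from the end of post-block testing to the first follow-up visit. That leaves 67-88% of the 24 h anesthetic effect and 83-94% of the first 48 h without a planned reading if monitoring lasts 3 to 8 h, and more if only the 60- or 90-minute periods apply. The BTX peak and the 4-week dose decision are covered.

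The number of events missed cannot be estimated, because neither the rate for this block in heart failure nor the share with symptoms is known. The conclusion rests on a damaged table, on the assumed 3 to 8 h, and on the lost-label row not being a pressure measurement. It is a cheap gap to narrow, not a failure of the dose-finding design.

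**What to change.** 1. At the existing 48-hour call, and at a week 1 call if Table 1 shows one, record a fixed set of items: dizziness on standing, faint, fall, and a home-cuff reading lying and standing. Enter them in the safety table.
2. List events inside the 24 h anesthetic period separately, so that they are not attributed to the BTX dose.
3. The investigators must reconcile Design & Procedures (90 minutes), Study Interventions (60 minutes), Risk/Benefit Assessment (several hours), the 24 h anesthetic effect in the nerve block section, and Table 1 on post-block observation.
4. They must also reconcile the down-titration trigger with the 4-week assessment and state which observation window the trigger uses.

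No monitoring length or dose rule is proposed here. A cuff reading at the call narrows the gap but does not fill it: events in the first day would still reach the record mainly through recall.

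The cost is protocol wording, a short call script and a home cuff for each subject. The downside is that more early events will be recorded, so the safety table may look less favourable.

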## Selection of Subjects

- List inclusion/exclusion criteria and how subjects will be identified.

Subjects will be identified by screening the Duke University Medical Center or Duke Raleigh outpatient heart failure and catheterization clinic environments. All study subjects will have an electively scheduled right heart catheterization, by the cardiologist, with or without an invasive cardiopulmonary exercise. Subjects with Cardiomems device will already have the device in place prior to the electively scheduled right heart catheterization.

### Inclusion Criteria:

1. Age 18-90
2. Patients with or without Cardiomems device implanted
3. Followed at DUMC for known or suspected diagnosis of HF (NYHA stage 2-3, Class C-D), including patients on inotropic medication
4. Systolic blood pressure (SBP) > 100mmHg
5. History of HF hospitalization or ER visit or IV diuretic use in the last 12 months.
6. Patients will be included regardless of left ventricular ejection fraction.

### Exclusion Criteria:

1. Contraindicated medications:

- Anticoagulation at the time the procedure or in case of recent warfarin use an INR >1.4. Anticoagulation includes: warfarin, or novel oral anticoagulants like dabigatran, rivaroxaban, apixaban, edoxaban or full dose intravenous heparin products or bivalirudin and fondaparinux). Antiplatelet agents besides aspirin such as ticagrelor, prasugrel, Plavix are also considered to be a contraindication if used at time point of procedure.
- Immunosuppressive medications for solid organ transplant

2. HF medication regimen: Initiation of HF medications (in the 48 hours preceding the study) such as beta blockers, ACEI, ARB, aldosterone receptor blockers, calcium channel blockers of any type, central sympatholytics like clonidine, moxonidine,

3. Recent acute MI or hemodynamic instability:

- Acute MI (STEMI or Type I NSTEMI) within 7 days.
- Evidence of progressive cardiogenic shock within 48 hours

4. Certain forms of HF:

- Restrictive cardiomyopathy
- Constrictive pericarditis
- Pericardial effusion with evidence of tamponade
- Severe valvular stenosis requiring intervention

5. Severe bleeding risk:

- Known history of an increased bleeding risk
- Thrombocytopenia (< 50,000)

6. Significant comorbidities:

- End-stage renal disease CKD stage 5 due to primary renal pathology
- Severe scoliosis of the thoracic spine
- History of lung disease other than asthma and COPD (like interstitial fibrosis, cystic fibrosis, pneumonitis, lung cancer etc.)
- Respiratory instability (dependent on >4 L nasal cannula for a saturation >90% SpO2)

- Exclude severe fixed pulmonary hypertension
- History of organ transplant (heart , lung, liver, pancreases, small bowel).

7. Pregnancy: patients of childbearing age will be tested with pregnancy tests, unless they had a hysterectomy or removal of their ovaries.

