**Splanchnic Nerve Block for Therapy of Chronic Heart Failure (Splanchnic III)**

**Clinicaltrials.gov number: NCT04575428**

**Duke IRB number: Pro00103788**

**Date: May 1th 2023**

## Research Abstract

### Please type your Research Abstract here:

The Research Abstract should summarize the main points of your study in one paragraph. The following guidelines may help you:

1. Purpose and objective (1-2 sentences)
2. Study activities and population group (2-4 sentences)
3. Data analysis and risk/safety issues (1-2 sentences)

Splanchnic vasoconstriction may contribute to decompensation of chronic heart failure (HF) via volume redistribution from the splanchnic vascular bed to the central compartment. This is a sympathetically mediated reflex and can be interrupted through a splanchnic nerve block (SNB). We hypothesize that interruption of the efferent/afferent innervation of the splanchnic vasculature will decrease cardiac congestion and improve renal function in patients presenting with HF.

We have already obtained preliminary safety and efficacy data in acute and chronic heart failure patients with temporary (<24 h) SNB. Now we would like to apply a prolonged SNB in chronic heart failure patients using a long acting agent.

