**Nerve Block Procedure.** The unilateral, left-sided, temporal bilateral celiac plexus block will be performed by the interventional pain specialty team in the catheterization laboratory, with continuous hemodynamic monitoring similarly to our previously published experience. The celiac plexus block will be performed under fluoroscopic guidance in the posterior chest wall (vertebral space L1) to guarantee maximal safety (**Figure 2**). We will use a mix of 3 ml of lidocaine 1.55 with 1:10000 epinephrine, 10 ml of 0.5% ropivacaine and up to 1.5 U/kg of BTX Type A. Lidocaine with epinephrine is used for procedural

safety to exclude intravascular injection. In the present study we will start at a lower dose of the BTX (dose finding). We will plan to increase dose or decrease per Kg unit doses for Botox based on 4 week assessment.

The dosing up titration scheme (Scenario 1) is as following:

1. The 1st and 2nd subject receiving the block splanchnic procedure - 75Units of Botox, (not more than 1.5 Units/kg) follow up at 2 weeks with CPX and 4 weeks with invasive CPX and 8 weeks with CPX
2. The 3rd and 4th subject receiving the block splanchnic procedure - if prior dose tolerated, no safety issues at 4 weeks than proceed with dose increase to: 100Units of Botox, (not more than 1.5Units/kg) follow up at 2 weeks with CPX and 4 weeks with invasive CPX and 8 weeks with CPX
3. The 5th and 6th subject receiving the block splanchnic procedure - Scenario 1: if prior dose tolerated, no safety issue and satisfactory efficacy at 4 weeks than patient 5/6 will get injection of 100Units of Botox again (not more than 1.5Units/kg) with follow up at 2 weeks with CPX and 4 weeks with invasive CPX and 8 weeks with CPX Satisfactory efficacy is defined as >25% reduction with exercise wedge pressure  
Scenario 2: if prior dose tolerated, no safety issue and efficacy not satisfactory at 4 weeks than patient 5/6 will get injection of 125Units of Botox (not more than 1.5Units/kg) with follow up at 2 weeks with CPX and 4 weeks with invasive CPX and 8 weeks with CPX.

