#### 8. Procedure

Unable to tolerate procedure as determined by or investigator

Will be excluded if invasive hemodynamics on study date determine that the does not have elevated filling pressures at rest or stress. Following pressures/situations will exclude the : wedge pressure < 15mmHg (< 12mmHg on inotrope) at rest and < 25mmHg with peak stress (< 22 with inotropes) and greater than the central venous pressure or determined by study personnel to be at risk for nerve block related complications.

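### No eligibility criterion names recent non-study botulinum toxin or a known neuromuscular or cholinergic-transmission disorder, although the study drug is a toxin with a stated effect lasting months

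*Combined protocol and SAP*

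**What the plan says.** The Research Abstract presents the toxin as the new element of this study: "Now we would like to apply a prolonged SNB in chronic heart failure patients using a long acting agent". Under Testing procedures, the Nerve Block Procedure text specifies a mix of lidocaine with epinephrine, ropivacaine and "up to 1.5 U/kg of BTX Type A". The planned doses are 75, 100 and possibly 125 units, with 50 units as a fallback. The same section says that "BTX is a neurotoxin that blocks cholinergic neurotransmission" and that "The estimated duration of BTX effect is up to 4-6 months".

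The Exclusion Criteria have eight numbered items. Item 1, "Contraindicated medications", has two bullets: anticoagulants with antiplatelets, and immunosuppression for organ transplant. Item 6 lists comorbidities, among them "Severe scoliosis of the thoracic spine". Item 8 adds haemodynamic thresholds and two judgement clauses. One concerns ability to tolerate the procedure; the other excludes anyone "determined by study personnel to be at risk for nerve block related complications".

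**The concern.** Two kinds of candidate deserve a question before this injection: someone whose cholinergic transmission is already impaired, and someone who recently received botulinum toxin for another reason. The protocol's own account of mechanism and duration points to both. As the criteria are written, either could be enrolled without anyone having asked.

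What is at stake is the safety of an individual subject. An injected toxin with an effect of months cannot be withdrawn if a problem appears, so screening is the main point of control. The Risk/Benefit Assessment reassures that mild complications settle as the anaesthetic wears off, but that refers to a drug expected to last 24 hours.

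**Working it through.** No figure in the plan is in dispute. The check is a reading of the criteria against the description of the drug, with one conversion of units.

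**1. Criteria that name the toxin or a related disorder.**

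| Place | Content | Names outside toxin? | Names a neuromuscular or cholinergic disorder? |
|---|---|---|---|
| Inclusion 1-6 | age, implanted monitor, heart failure, blood pressure, recent event, ejection fraction | no | no |
| Exclusion 1 | anticoagulants and antiplatelets; transplant immunosuppression | no | no |
| Exclusion 2 | heart failure drugs started in the prior 48 hours | no | no |
| Exclusion 3-5 | recent infarction or shock; certain forms of heart failure; bleeding risk | no | no |
| Exclusion 6 | renal, spinal, lung, respiratory, pulmonary hypertension, transplant | no | no |
| Exclusion 7 | pregnancy | no | no |
| Exclusion 8 | tolerance, filling pressures, judged risk of block complications | no | no |

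The count is 0 in each column. Two clauses in item 8 are general enough to be used case by case.

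**2. Time scale.** With 30.44 days per month:
- 4 months = 4 × 30.44 / 7 = 17.4 weeks.
- 6 months = 6 × 30.44 / 7 = 26.1 weeks.
- The ropivacaine effect is put at 24 hours. The stated toxin effect is therefore about 122 to 183 times as long (4 × 30.44 = 122 days; 6 × 30.44 = 183 days).

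The only look-back for recent drug use that the list sets as a fixed interval is the 48 hours in item 2.

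**3. Dose cap.** The limit of 1.5 U/kg, with a highest step of 125 units, applies to the study injection. It takes no account of toxin received elsewhere.

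**4. Prior experience cited.**
- Risk/Benefit Assessment: "We have now completed 28 cases in the first pilot trial using lidocaine/ropivacaine and found no acute or chronic complications". These cases did not use the toxin.
- Background & Significance: one published case of toxin at the celiac plexus or splanchnic nerves, for refractory hypertension.
- Same section: the group's own use of toxin in epicardial fat pads to prevent atrial fibrillation after surgery. This is autonomic use of the toxin, but at another site.

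Nothing is said in any of these about subjects with prior toxin or a cholinergic disorder.

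**5. Prompts to ask.** The complications in the Risk/Benefit Assessment are anaesthetic toxicity, needle injury, hypotension, gut dysmotility, pain and bleeding. No toxin-specific risk is described. No section sets a washout or a screening question for outside toxin.

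**The case against.** The strongest reply is item 8. The block in this protocol is the whole injected mix, so a toxin complication is a block complication, and staff may exclude anyone they judge at risk. The injection is given by an interventional pain team that may well take such a history unprompted. This stands in part: the clause gives staff the power to exclude. It does not tell them to ask, names no toxin-related condition and sets no time window, so it softens the gap without closing it.

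Four stronger readings are tempting and are not supported.

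- *The toxin is the one agent left out of an otherwise tailored list.* It is not. No item covers sensitivity to lidocaine, ropivacaine or epinephrine either, although anaesthetic toxicity is named as a risk.
- *Recent toxin at another site is shown to be hazardous.* The documents describe an effect after local injection and do not say that toxin elsewhere adds to it. Carrying the 4 to 6 months over to other sites is an assumption. The disorder half of the point follows more directly from the stated mechanism.
- *Residual toxin would distort the dose steps or the efficacy results.* The documents give no basis for this, and it is not claimed.
- *The group has almost no relevant toxin experience.* The epicardial work counts as experience, though it does not address these subjects.

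Consent pages are absent from the public file and may carry a warning. A warning there would not be an eligibility criterion.

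**Conclusion.** The point holds as a minor, inexpensive subject-safety gap in the criteria as written. A candidate with a known neuromuscular or cholinergic-transmission disorder, or with recent outside toxin, is eligible unless staff learn of it and apply their discretion.

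The conclusion rests on the protocol's own statements of mechanism and duration, and on the inference that impaired cholinergic transmission is a reason for caution. For outside toxin it rests also on the precautionary assumption that the stated duration is a sensible guide at other sites. How often such candidates present, and how much risk they would carry, cannot be estimated from the documents.

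**What to change.** 1. Add to exclusion item 6: *known neuromuscular or cholinergic-transmission disorder*, with the exact terms set by the clinical team.
2. Ask every candidate before the block about prior botulinum toxin, and record date, dose and site.
3. As a precaution, add to exclusion item 1: *botulinum toxin within 6 months before the block*. This takes the upper end of the protocol's own duration estimate.

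Questions about toxin use after the block could be added at existing visits and phone calls. That is optional and not needed to close this gap.

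The cost is two lines of criteria and one history question, with no new test or visit. The downside is that a few candidates may be lost, or delayed by up to 6 months; the documents do not allow a count.
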